Appendix 2. Statistical Analysis Plan for Continuous Glucose Monitoring (CGM)

Continuous glucose monitoring (CGM) will be performed in a subset of patients in Study I8B-MC-ITSB (ITSB) in order to evaluate the 24-hour glucose profile captured with CGM for LY900014 and Humalog, when either is used in combination with basal insulin as part of a multiple daily injection regimen. In 2 of the treatment groups, LY900014 and Humalog will be administered immediately (0 to 2 minutes) prior to each meal in a double-blind manner. A third open-label treatment group consists of LY900014 administered up to 20 minutes after the start of a meal (LY900014 +20). These 3 treatment groups are denoted as LY900014, Humalog and LY900014+20 in the study objectives.

This appendix provides the statistical analysis plan for the CGM addendum I8B-MC-ITSB(3.1). The target range for #3 objective has been changed from “71 to 180 mg/dL” to “70 to 180 mg/dL” to reflect the recommendations set forth in the “Clinical Targets for Continuous Glucose Monitoring Data Interpretation: Recommendations From the International Consensus on Time in Range” (Battelino et al. 2019). Similarly, one of the cut points for #5 objective has been changed from “ ≤ 70 mg/dL” to “ < 70 mg/dL.”

Appendix 2.1. Objectives and Endpoints for CGM Addendum

Table APP.2.1 shows the objectives and endpoints for CGM addendum.

Table APP.2.1. Objectives and Endpoints for CGM Addendum

Objectives	Endpoints
Primary Objective	
1. To compare LY900014 and Humalog, when administered as prandial insulin (0 to 2 minutes prior to the start of a meal), with respect to the incremental glucose AUC0-2hours after the start of meals	1. Incremental AUC0-2hours after the start of meals from up to 10 days of continuous glucose monitoring (CGM) use at Week 26
Secondary Objective	
2. To compare LY administered as postprandial insulin up to 20 minutes after the start of a meal (LY900014 +20) and Humalog with respect to the incremental AUC0-2hours after meals	2. Incremental AUC0-2hours after the start of meals from up to 10 days of continuous glucose monitoring (CGM) use at Week 26
3. To compare LY900014, LY900014 +20 and Humalog with respect to the duration of time glucose values are within target range 70 to 180 mg/dL (3.9 and 10.0 mmol/L) during daytime.	3. Duration (in minutes) and percentage of time with glucose values within target range 70 to 180 mg/dL (3.9 and 10.0 mmol/L) during daytime, both inclusive, normalized to daytime period from up to 10 days of CGM use at Week 26
4. To compare the glucose excursions after meal between LY900014, LY900014 +20, and Humalog	4. Average glucose excursions 0 to 1, 2, 3, 4 hours after the start of meals, from up to 10 days of CGM use at Week 26

Objectives and Endpoints for CGM Addendum

Objectives	Endpoints
5. To compare LY900014, LY900014 +20, and Humalog with respect to the duration of time spent in hypoglycemic glucose ranges	5. Duration (in minutes) and percentage of time with glucose values <54, and <70 mg/dL (3.0 and 3.9 mmol/L) normalized to a 24-hour period from up to 10 days of CGM use at Week 26
6. To compare LY900014, LY900014 +20, and Humalog with respect to the duration of time spent in hyperglycemic glucose ranges	6. Duration (in minutes) and percentage of time with glucose values >180 mg/dL (10.0 mmol/L) normalized to a 24-hour period from up to 10 days of CGM use at Week 26
7. To compare LY900014, LY900014 +20, and Humalog with respect to the glucose variability during daytime	7. Blood glucose risk index during daytime from up to 10 days of CGM use at Week 26

Appendix 2.2. General Considerations

The Dexcom G6® Continuous Glucose Monitoring System (Dexcom G6) will be used in CGM addendum I8B-MC-ITSB(3.1). Patients who choose to participate in the Study ITSB CGM addendum (3.1) will use the Dexcom G6 system during 2 periods of time, prior to baseline and prior to the 26-week primary endpoint. The Dexcom G6 will be worn for up to 10 consecutive days per period.

The CGM Population includes all randomized patients who have an informed consent for the CGM addendum signed by parent(s)/legal guardian(s) and valid CGM data at baseline (Visit 4) or primary endpoint (Visit 15). Unless otherwise specified, the analyses of the CGM addendum will use the CGM Population. The data collected after permanent discontinuation of investigational product or during days when patients are temporarily off study treatment will be excluded. There will be no multiplicity adjustment.

To ensure that the CGM outcome variables are only calculated from valid CGM days with sufficient data within the 24-hour, the following criterion will be used to determine a valid CGM day: minimum number of measures per day – at least 70% of the total measures (288 measures per day) that are supposed to be obtained. All the CGM derivations are based on the data from the valid CGM days with sufficient data defined above unless otherwise specified.

Patients will be instructed to capture the start time of 3 main meals (morning meal, mid-day meal, evening) when accompanied by prandial insulin dose during each CGM session in the patient CGM diary page. The start time will be used to derive the CGM meal related outcomes for each meal and across all meals. On valid CGM days, the meal related outcomes will also use the 70% cut-point to determine a valid CGM session for the variable derivation. For example, the $iAUC_{0-2hr}$ after the morning meal for a day requires at least 70% of the 24 measures (ie, at least 17 measures) during the 2 hour time window after the start of the morning meal. If the analysis time window covers the start time of the next meal (assuming $TN0$ relative to the start time of the given meal and $TN0 < T$) and the number of non-missing measures within 0 to $TN0$ is greater than 70% of measures within 0 to T , the derivation of the meal related outcomes within 0 to T

will be based on the data from time 0 to *TNO*. Only the first meal of each type per day will be included in derivations

All CGM outcome variables will be derived for each patient for each visit, based on the valid CGM data described above. The data will be summarized by visit and by treatment group.

For continuous measures, summary statistics will include sample size, mean, standard deviation (SD), median, minimum, and maximum for both the actual and the change from baseline measurements. Least-squares (LS) means and standard errors derived from the analysis models will also be provided. Treatment comparisons will be evaluated by the treatment difference LS means, the 95% CIs for the treatment differences, and the p-values for the treatment comparisons.

For categorical measures, summary statistics will include sample size, frequency, and percentages. Fisher's exact test or Pearson's chi-square test will be used for treatment comparisons, unless otherwise specified.

A listing of all randomized patients with CGM addendum-specific informed consent form and did or did not wear the blinded Dexcom G6 at least once during the study will be produced. The listing will contain the dates that patients started and stopped wearing the Dexcom G6 for each visit during the study.

Additional analyses not specified in this SAP may be conducted, if deemed necessary.

Appendix 2.3. Baseline Characteristics

The following analyses planned for the main study (Section 5.7) will be repeated for the CGM Population:

- summaries of baseline and diabetes characteristics
- a listing of patients whose stratification factor value entered into the interactive web-response system (IWRS) is different from the clinical database
- a listing of patient characteristics at baseline

Appendix 2.4. Primary CGM Outcome and Methodology

The primary outcome of the CGM addendum is the iAUC0-2hr after meals obtained from up to 10 days of CGM use at Week 26. The derivation of the iAUC0-2hr for each visit is outlined in [Appendix 2.8](#).

An ANCOVA model with treatment, type of basal insulin, hemoglobin A1c (HbA1c) stratum [$\leq 8.0\%$ or $> 8.0\%$], and age group as fixed effects and baseline as a covariate will be used for treatment group comparison. At Week 26, the treatment difference and LS mean of the difference estimated from the model will be provided.

If the percentage of the patients with missing baseline values is higher than 20% of the CGM Population, a constrained longitudinal data analysis model (Liu et al. 2009; Lu 2010) will be used instead. An unstructured covariance structure will be used to model the within-patient

errors. If this analysis fails to converge, the following covariance structures will be tested in order:

- compound symmetry with heterogeneous variances
- compound symmetry without heterogeneous variances.
- First order autoregressive

The first covariance structure that converges will be used. The Kenward–Roger approximation will be used to estimate denominator degrees of freedom.

Appendix 2.5. Secondary CGM Variables and Analysis

The following variables will be derived from the original data collected through the CGM device and will be compared LY900014, LY900014+20 and Humalog at Week 26 using the similar model as the primary analysis in [Appendix 2.4](#):

- incremental AUC 0-2 hours after the start of meals (across all three main meals)
- duration (in minutes) and percentage of time with glucose values between 70 and 180 mg/dL (3.9 and 10.0 mmol/L) (both inclusive) during daytime (defined as 0600 to midnight), normalized to a 24-hour period
- average glucose excursions 0 to 1 hour after the start of meals (across all 3 main meals)
- average glucose excursions 0 to 2 hours after the start of meals (across all 3 main meals)
- average glucose excursions 0 to 3 hours after the start of meals (across all 3 main meals)
- average glucose excursions 0 to 4 hours after the start of meals (across all 3 main meals)
- duration (in minutes) and percentage of time with glucose values <54 (3.0 mmol/L) normalized to a 24-hour period
- duration (in minutes) and percentage of time with glucose values <70 mg/dL (3.9 mmol/L) normalized to a 24-hour period
- duration (in minutes) and percentage of time with glucose values >180mg/dL, (10.0 mmol/L) normalized to a 24-hour period
- blood glucose risk index during daytime (0600 to midnight)

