4. To compare LY900014, LY900014 +20, and Humalog with respect to the incidence and rate of documented post-dose hypoglycemia	4. Rate (events/patient/year) and incidence (percent of patients with events) of documented post-dose hypoglycemic events within 1 and 2 hours after the prandial dose from Week 0 through Week 26
5. To compare LY900014, LY900014 +20, and Humalog with respect to the incidence and rate of documented hypoglycemia	5. Rate (events/patient/year) and incidence (percent of patients with events) of documented hypoglycemic events from Week 0 through Week 26
6. To compare LY900014, LY900014 +20, and Humalog on the rate of severe hypoglycemic events	6. Rate (events/patient/100 years) of severe hypoglycemic events from Week 0 through Week 26

Objectives and Endpoints

Objectives	Endpoints
7. To compare LY900014, LY900014 +20, and Humalog with respect to total, basal, and prandial insulin dose	7. Change from baseline in total, basal, and prandial insulin doses and prandial/total insulin dose ratios at Week 26
8. To compare LY900014, LY900014 +20, and Humalog with respect to the proportion of patients achieving HbA1c targets	8. The proportion of patients with HbA1c <7% and <7.5% at Week 26
9. To compare LY900014, LY900014+20, and Humalog with respect to 7-point SMBG	9. Change from baseline to Week 26 in 7-point SMBG values
Tertiary/Exploratory Objectives	
10. To compare LY900014, LY900014 +20, and Humalog with respect to changes in body weight	10. Change in weight (kg) from baseline to Week 26
11. To compare LY900014, LY900014 +20, and Humalog with respect to glycemic variability	11. Within-day and between-day glycemic variability measured by the standard deviation and the coefficient of variation of 7-point SMBG profiles
12. To compare the incidence of treatment-emergent positive anti-insulin lispro antibodies for LY900014, LY900014 +20, and insulin lispro	12. Incidence of treatment-emergent positive anti-insulin lispro antibodies

Abbreviations: HbA1c = hemoglobin A1c; NIM = noninferiority margin; SMBG = self-monitored blood glucose; T1D = type 1 diabetes.

5. A Priori Statistical Methods

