Appendix 2.8.5. Within-day glucose variability

For variables assessing within-day variability, first determine the variability within each valid CGM day, then average across all valid CGM days within a visit.

Within-day glucose SD (Hirsch 2005; Rodbard 2009):

$$SD = \frac{1}{m} \sum_{k=1}^m SD_k = \frac{1}{m} \sum_{k=1}^m \sqrt{\frac{\sum_{i=1}^n (BG_{k,i} - \frac{\sum_{i=1}^n BG_{k,i}}{n})^2}{n-1}}$$

Within-day glucose CV (Clarke and Kovatchev 2009):

$$CV = \frac{1}{m} \sum_{k=1}^m CV_k = \frac{1}{m} \sum_{k=1}^m \frac{SD_k}{\frac{\sum_{i=1}^n BG_{k,i}}{n}} \times 100$$

Inter-quartile range (IQR) [Mazze et al. 2008]:

$$IQR = \frac{1}{m} \sum_{k=1}^m IQR_k = \frac{1}{m} \sum_{k=1}^m (75\text{th} - 25\text{th percentile of all BG values on day } k)$$

The low blood glucose index (LBGI) has been developed to quantitate both frequency and severity of hypoglycemia. The LBGI has been validated as a predictor of severe hypoglycemia. The HBGI quantifies both frequency and severity of hyperglycemia and has been related to HbA1c and risk for hyperglycemia (Kovatchev et al. 2005). Additionally, both the LBGI and high blood glucose index (HBGI) have a high sensitivity to changes in glycemic profiles and control (Kovatchev et al. 2005). Low blood glucose index is a non-negative number that increases as the number of low readings increases. High blood glucose index is a non-negative number that increases as the number of high readings increases.

The LBGI, HBGI, and blood glucose risk index (BGRI) will be derived for each valid CGM day of a visit in the following steps:

Step 1: For each blood glucose (BG [mg/dL]) at the i^{th} time point, compute the following:

$$f(BG_i) = 1.509 \times [(\ln(BG_i))^{1.084} - 5.381]$$

This transforms the BG data using a nonlinear transformation that maps the BG range of 20 to 600 mg/dL to a symmetric interval of $(-\sqrt{10}, \sqrt{10})$

The center of the BG scale is 112.5 mg/dL and is mapped to 0

Step 2: Compute BG risk for each reading

$$rl(BG_i) = 10 \times f(BG_i)^2 \text{ if } f(BG) < 0; \text{ otherwise } rl(BG_i) = 0$$

$$rh(BG_i) = 10 \times f(BG_i)^2 \text{ if } f(BG) > 0; \text{ otherwise } rh(BG_i) = 0$$

Assign the risk of each BG value by applying the above quadratic risk function

Value range from 0 (achieved when BG = 112.5, the center) to 100

Left side of the parabola is risk of hypoglycemia, and the right side is risk of hyperglycemia

Step 3: Compute LBGI and HBGI

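### CGM objective 7 asks about daytime glucose variability, but the only variable assigned to it, the blood glucose risk index, mixes mean glucose with spread

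*SAP*

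**What the plan says.** SAP Table APP.2.1, row 7, compares the three arms "with respect to the glucose variability during daytime". The one endpoint beside it is "Blood glucose risk index during daytime from up to 10 days of CGM use at Week 26".

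Appendix 2.5 lists the variables to be compared between arms at Week 26 with a model like the ANCOVA of Appendix 2.4. The only entry there that serves objective 7 is "blood glucose risk index during daytime (0600 to midnight". No SD, CV, IQR, MAGE or MODD appears in that list.

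Appendix 2.8.5 defines BGRI as LBGI plus HBGI and fixes the zero of the scale: "The center of the BG scale is 112.5 mg/dL and is mapped to 0". It also says what one component measures: "The HBGI quantifies both frequency and severity of hyperglycemia and has been related to HbA1c and risk for hyperglycemia".

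Appendices 2.8.4, 2.8.5 and 2.9 derive within-day SD, CV, IQR and MAGE, and between-day SD, CV and MODD, each for daytime as well as other periods. The main study treats variability differently: objective 11 in Table ITSB.4.1 is "Within-day and between-day glycemic variability measured by the standard deviation and the coefficient of variation of 7-point SMBG profiles".

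**The concern.** A variability measure should describe how far readings scatter around the patient's own average. BGRI scores each reading against a fixed glucose level, so a patient who is steadily high scores badly with no scatter at all.

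If one arm ends with a different mean glucose, which HbA1c already reflects, BGRI will differ even when variability does not. Reported under objective 7, that difference would be described as a variability finding. The measures that would separate the two are computed, but none is named as the comparison for this objective. Choosing among them after unblinding would be post hoc.

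**Working it through.** **Inputs from the SAP (Appendix 2.8.5).** f(BG) = 1.509 × [(ln BG)^1.084 − 5.381]. The risk of a reading is 10 × f². It counts towards LBGI if f < 0 and towards HBGI if f > 0. BGRI = LBGI + HBGI.

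**1. Reproduce the plan's calibration.** The SAP says 20 to 600 mg/dL maps to ±√10 = ±3.162, 112.5 maps to 0, and risk runs from 0 to 100. The formula gives f(20) = −3.163, f(112.5) = −0.0003 and f(600) = +3.161, with risks 100.0, 0.0 and 99.9. The scale is as described.

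**2. Split the index.** Every reading falls in LBGI or HBGI, so BGRI is the mean of 10 × f² over the readings. Hence

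BGRI = 10 × mean(f)² + 10 × var(f).

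The first term is level and the second is spread.

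**3. Flat profiles, where spread is zero.** At 180 mg/dL, f = 0.879, so BGRI = 10 × 0.879² = 7.7. In the same way BGRI is 1.7 at 140, 4.3 at 160, 11.6 at 200 and 22.4 at 250.

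**4. Share of BGRI due to spread.** The documents give no expected sensor mean or CV, so these are assumptions: readings clipped to 40–400 mg/dL, CV 40%, lognormal or gamma.

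| Mean (mg/dL) | Spread share, lognormal | Spread share, gamma |
|---|---|---|
| 140 | about 88% | 90% |
| 160 | 66% | 70% |
| 180 | 48% | 53% |
| 200 | 37% | 41% |
| 220 | 28% | 33% |

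**5. Response to mean and to spread** (lognormal, same clipping).

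- At CV 35%, means of 170, 180 and 190 give BGRI of about 8.4, 10.0 and 11.6.
- At mean 180, raising CV from 35% to 45% gives 10.0 to 11.2. Near 180, a 10 mg/dL rise in mean moves BGRI by about 1.6, and a 10-point rise in CV by about 1.2.
- At mean 140, raising CV from 25% to 45% takes BGRI from about 3.3 to 6.9, so it doubles. At mean 160 the same change takes it from about 5.7 to 8.7.

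**6. Reversal of order.** Mean 190 with CV 30% (SD 0.30 × 190 = 57) gives about 11.1. Mean 180 with CV 40% (SD 0.40 × 180 = 72) gives about 10.6. The profile with the smaller SD and the smaller CV has the higher BGRI.

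**7. Correlation across simulated patients** (assumed populations, lognormal readings, clipped).

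| Patient mean (SD), CV (SD) | BGRI with mean | BGRI with SD | BGRI with CV |
|---|---|---|---|
| 185 (30), 36% (6%) | 0.97 | 0.73 | −0.06 |
| 150 (25), 38% (6%) | 0.82–0.88 | 0.83–0.86 | 0.28–0.30 |

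Ranges are across separate runs. With mean 190 (SD 35) and CV 40% (SD 4%), the correlation with CV falls to −0.45. Part of the weak link with CV comes from the clipping, which lowers realised CV in patients with high means.

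**The case against.** The case for leaving the plan alone has four parts.

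- **BGRI does respond to variability.** Variance is one of its two terms. A reader of the flat-profile figures might infer that BGRI barely reacts to spread, but step 5 shows otherwise at 140 and 160 mg/dL. In the 185 mg/dL population, its partial correlation with CV at fixed mean is about 0.6. The titration targets in protocol Table ITSB.4 and the absence of a lower HbA1c limit for entry mean that lower sensor means cannot be ruled out. This stands. Only at about 200 mg/dL and above does BGRI follow mainly the mean.
- **Other measures will be available.** A reader might infer that objective 7 cannot be answered. Appendix 2.2 summarizes all derived CGM variables by visit and arm, and its general text for continuous measures provides LS mean differences, confidence intervals and p-values. Daytime SD, CV, IQR and MAGE will therefore be visible. This also stands. What remains is that no section ties any of them to objective 7, and only the Appendix 2.5 variables are explicitly assigned a model.
- **The plan is internally consistent.** Objective, endpoint, formula and model match, and Appendix 2.9 files BGRI under within-day variability. The addendum protocol, which may justify the choice, is not among the documents. This stands as a matter of labelling, but a label does not change what the formula measures.
- **The main study covers variability by SD and CV.** It does so from fingerstick profiles under a different objective. That does not fill the gap for CGM, and it shows which measures the sponsor uses elsewhere.

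**Conclusion.** The point holds in limited form. The only endpoint named for objective 7 confounds mean glucose with spread, so a BGRI difference by itself is not evidence of a variability difference in either direction.

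The decomposition and the flat-profile scores follow from the SAP formula and need no assumption. The spread shares, the reversal and the correlations depend on assumed means, CVs and distributions. They range from mostly spread near 140 mg/dL, through about half at 180, to mostly level at 200 and above.

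The documents do not support the stronger statements that BGRI is insensitive to variability or that the objective is unanswerable. The consequence is confined to one secondary objective of a CGM subset addendum that has no multiplicity adjustment. The primary and gated HbA1c conclusions and the addendum's primary iAUC comparison are untouched.

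**What to change.** In Table APP.2.1 row 7 and in Appendix 2.5, add daytime (0600 to midnight) within-day CV, with SD beside it, as the pre-specified variability comparison for objective 7, using the same model as the other secondary CGM variables. Give both, because CV is itself a ratio to the mean. Keep BGRI, show LBGI and HBGI separately, and label all three as glycemic risk. If the sponsor prefers BGRI as the sole endpoint, retitle objective 7 as glycemic risk.

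The cost is SAP wording, made before unblinding, and one or two more ANCOVAs on variables already derived. The downside is one or two more unadjusted comparisons. The SAP has already changed glucose cut points for CGM objectives 3 and 5 (introduction to Appendix 2), so an edit of this kind has a precedent.

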Appendix 2.6. Additional Analyses

The following key efficacy and safety outcomes collected in the main study (not through CGM addendum) will be analyzed using the CGM Population:

- HbA1c at Week 26
- incidence and rate of documented hypoglycemic events from Week 0 to Week 26
- incidence and rate of nocturnal hypoglycemic events from Week 0 to Week 26
- incidence and rate of non-nocturnal hypoglycemic events from Week 0 to Week 26s
- incidence and rate of severe hypoglycemic events from Week 0 to Week 26

- change from baseline in total, basal and prandial insulin dose, and the ratio of prandial and total insulin dose at Week 26

The analysis methods for the above outcomes will be the same as those specified in Section 5.

Proportion of patients who have achieved the guidance (Battelino et al. 2019) recommended CGM targets of glycemic control (see Table APP.2.2) at Week 26 will also be summarized by treatment and analyzed using logistic regression model with treatment, age group and baseline as covariates.

Table APP.2.2. Guidance Recommended CGM Targets of Glycemic Control

Percentage of time with sensor glucose (24-hour)	Guidance Recommendation
target range	
70-180 mg/dL (3.9-10.0 mmol/L, both inclusive)	>70%
hypoglycemia range	
<70 mg/dL (3.9 mmol/L)	<4%
<54 mg/dL (3.0 mmol/L)	<1%
hyperglycemia range	
>180 mg/dL (10.0 mmol/L)	<25%
>250 mg/dL (13.9 mmol/L)	<5%

